- o Individuals with specific conditions that increase the risk for severe RSV as defined by the CDC during the baseline period, identified as those with chronic cardiovascular disease, chronic lung or respiratory disease, end-stage renal disease or dependence on hemodialysis or other renal replacement therapy, diabetes mellitus with complications, neurologic or neuromuscular conditions causing impaired airway clearance or respiratory muscle weakness, chronic liver disease, chronic hematologic conditions, severe obesity, moderate or severe immune compromise, residence in a nursing home, or other chronic medical conditions or risk factors that a health care provider determines would increase the risk for severe disease due to viral respiratory infection (eg, frailty);¹⁹ list of conditions may be updated to align with the most current CDC definition at the time of data analysis;
- o Different age groups defined by age on the index date, eg, 60 to 69 years, 70 to 79 years, ≥80 years;
- Individuals enrolled in the VHA with dual insurance coverage who are also identified in the Centers for Medicare & Medicaid Services (CMS) Medicare administrative claims data;

Data sources: The VHA is the largest integrated health care system in the US, providing both inpatient (IP) and outpatient (OP) clinical care to over 9 million Veterans enrolled at more than 170 medical centers and 1,113 community-based OP clinics.²⁰ The objectives of this study will be addressed using data from VHA's Corporate Data Warehouse (CDW), which is an integrated EHR system with a centralized data warehouse that is updated on a daily basis. The CDW lacks information on care received outside of a VHA facility. In a subgroup analysis of individuals with both VHA and Medicare coverage, CDW data will be supplemented and linked with Medicare administrative claims data at the patient level to ensure a more comprehensive evaluation of the care an individual receives.

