9.2.3. Subgroups

Safety surveillance may be conducted for subgroups of interest as applicable to each age group, including, but not limited to the ones described below.

The following subgroups will be analyzed for the 18-59 years old age group and the 60 years and older age group:

- Individuals in VA priority group 1; These individuals have either the highest levels of service connected disability (≥50% disabling), are considered unemployable, or have received the medal of honor. Individuals categorized as priority group 1 are the highest priority for VHA care. This will ensure that the individual is more likely to receive all of their care from a VA facility;
- Females enrolled in the VHA (pending sufficient sample size);

• Individuals with co-administration with other vaccines (ie, influenza vaccine, COVID-19 vaccine, or other pre-specified vaccines [eg, shingles, hepatitis B] listed in Section 9.3.3) on the same day.¹⁸

The following subgroups will be analyzed for the 60 years and older age group only:

- Individuals with specific conditions that increase the risk for severe RSV as defined by the CDC during the baseline period; list of conditions may be updated to align with the most current CDC definition at the time of data analysis (see Section 9.2.1);
- Different age groups defined by age on the index date, eg, 60 to 69 years, 70 to 79 years, ≥80 years;
- Individuals enrolled in the VHA with dual coverage who are also identified in the Centers for Medicare & Medicaid Services (CMS) Medicare administrative claims data, which will be linked to the Corporate Data Warehouse (CDW) to supplement the data for a more complete evaluation of healthcare encounters.

Additional subgroups of interest may be assessed as additional information becomes available from ongoing clinical trials, Vaccine Adverse Event Reporting System (VAERS), and other sources that will inform the ABRYSVO safety profile.

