9.4. Data Sources

The VHA is the largest integrated health care system in the US, providing both IP and OP clinical care to over 9 million Veterans enrolled at more than 170 medical centers and 1,113 community-based OP clinics. ²⁰ VHA's health care delivery system is organized regionally around 18 Veterans Integrated Service Networks (VISNs) across the US. Each VISN is responsible for health care planning and resource allocation in a particular geographical region. For example, VA New England Healthcare System (VISN 1) covers VHA facilities in Massachusetts, Connecticut, New Hampshire, Maine, and Rhode Island, while VA Heart of Texas Health Care Network (VISN 17) oversees the facilities in Texas. The VHA also maintains its own mortality data where 99% of enrollees' deaths are reported within one month of occurrence.

The objectives of this study will be addressed using data from VHA's CDW, which is an integrated EHR system with a centralized data warehouse that is updated on a daily basis. The CDW stores data in separate databases, one for each type of clinical information (eg, IP medication, IP admission, OP medication, OP visit). Individual demographic information such as date of birth and gender are also available. Immunization records include information on manufacturer, lot number, injection site, and history of immunizations. The CDW lacks information on care received outside of a VHA facility.

Each individual is assigned a unique identification number to allow for longitudinal follow-up as well as to cross-reference to the various separate databases. For example, in each IP admission record, there is information on the primary discharge diagnosis (and as many as 15 secondary diagnoses), date of admission, date of discharge, and length of stay. This record can then be linked to other information of that IP stay located in other files,

including procedures that the patient underwent during the hospitalization, medical specialty of the provider, and prescriptions dispensed. Other files are similarly structured, and therefore may be linked together to provide comprehensive information about the patient and his/her medical encounters.

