The VHA database is an appropriate data source to evaluate the safety of the ABRYSVO vaccine for the following reasons. First, VHA data are refreshed daily and would thus enable early data analysis. Second, the VHA population is on average older than the general US population.⁵⁴ Of these, about 30% (roughly 1,000,000 individuals) use VHA health services almost exclusively (ie, those with a priority group of 1 or 4; Veterans assigned to priority group 4 are either accepting VA assistance or housebound benefits, or have been determined to be "catastrophically disabled" by the VA.⁵⁵), which lends itself to having complete, longitudinal healthcare data for such individuals who may be at higher risk of RSV.^{56,57} These priority groups include Veterans with the highest levels of service-connected disability and are therefore, the highest priority for VHA care.⁵⁵ Finally, the VHA population has, on average, more comorbid conditions than the general population, which also indicates that these individuals may be at higher risk of RSV.⁵⁸ While the VHA population is predominantly male (approximately 90%), and thus lacks generalizability to females, it will still provide a useful setting to examine real-world vaccine safety.

Since it is possible that individuals may not have all their health encounters within the VHA, (especially older veterans who are also covered by Medicare), the CDW data will be supplemented with data from CMS as a subgroup analysis, linking Medicare administrative claims data at the patient level to ensure a more comprehensive evaluation of the care an individual receives. Medicare data will include eligibility files and claims for Fee-For-Service (FFS) billable healthcare services received in the IP and OP setting, as well as skilled nursing facility (SNF), hospice, and home health agencies, and will cover the US primarily among those 65 years of age and older. Medicare FFS claims data are comprised of six different types of data files, with a unique identifier for each beneficiary, allowing linkage across all data files. Below is a summary of the different datasets:

Master Beneficiary Summary File (MBSF): This dataset contains information on beneficiary enrollment for each calendar month in Medicare Parts A, B, and D. Eligibility for sample selection, including original and current enrollment reason, and baseline characteristics, specifically demographic information, will be obtained from these data files.

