However, there are several limitations when relying on VHA data that should be noted. First, there could be gaps in the data since individuals may receive healthcare services outside of VHA facilities. As such, if individuals receive ABRYSVO outside of a VHA facility, this information will not be captured in the VHA EHR system. Other medical information may be similarly under-captured in the VHA EHR system if the individuals seek care in non-VHA facilities, resulting in potential residual confounding. For example, veterans with secondary insurance or veterans who are 65 years of age and older who have Medicare may receive health care services outside of VHA facilities. One study on VHA enrollees in seven different states found that of all individuals admitted to VHA hospitals in 2007, one fifth also had a non VHA hospitalization during that year. 80 Another study reported that about 53% of Veterans 65 years of age or older who were dually eligible for VHA and Medicare services in 2003 and 2004 used both.⁸¹ Hence, it is important to note that data on vaccination status and clinical information may be incomplete. As such, the CDW data will be supplemented and linked with Medicare administrative claims data at the patient level for adults 60 years and older to ensure a more comprehensive evaluation of the care an individual receives. Linking variables are available in the data to allow for patient-level linking of the two data sources. Given the older age of many veterans, it is likely that these individuals have secondary coverage with Medicare. Additionally, subgroup analysis will be conducted among priority group 1 Veterans who are most likely to receive all of their care from a VA facility to ensure data completeness among individuals aged 18-59 years old.

Lastly, to the extent that the individuals in the VHA database are different from individuals outside of the VHA, the results may not be generalizable to the broader US population. For example, since the VHA includes predominantly male Veterans (approximately 90% male), findings from this study may not be generalizable to women in the US.

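### Medicare linkage is the plan's answer to missing outside care, but it is applied only in a subgroup whose people also differ, so its results cannot show how far missing care distorts the main 60+ atrial fibrillation incidence

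*Protocol*

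**What the plan says.** Section 9.4 names the CDW as the source for the study objectives and states: "The CDW lacks information on care received outside of a VHA facility". Section 9.9 accepts that "data on vaccination status and clinical information may be incomplete". It cites a study in which about 53% of dually eligible Veterans aged 65 or older used both systems in 2003-2004, and gives Medicare linkage as the consequence, describing it as applying to adults from age 60.

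Elsewhere the linkage is narrower. Section 9.4 says "the CDW data will be supplemented with data from CMS as a subgroup analysis". The Abstract says: "In a subgroup analysis of individuals with both VHA and Medicare coverage, CDW data will be supplemented and linked with Medicare administrative claims data". Section 9.2.3 lists, for the 60+ group only, VHA enrollees with "dual coverage who are also identified in the Centers for Medicare & Medicaid Services (CMS) Medicare administrative claims" data, the link serving "to supplement the data for a more complete evaluation of healthcare encounters". Section 9.4 adds that the Medicare files hold fee-for-service claims and "will cover the US primarily among those 65 years of age and older".

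Section 9.7.3 refits the propensity weights in each subgroup and otherwise applies the main methods. The primary objective in section 8 is the incidence of AF after vaccination.

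**The concern.** Incomplete capture can push AF incidence in two opposite directions. AF diagnosed outside VHA is missed, which lowers the rate. AF already diagnosed outside VHA during the two-year clean window is not seen, so a later VHA code looks like new onset, which raises the rate. The confirmatory diagnosis within 30 days can also be lost if it is made elsewhere.

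The linked data could measure each of these errors. As planned, though, people and data source change in the same step. If the linked subgroup differs from the main 60+ result, the cause may be the extra data or the different people. If it agrees, the errors may have cancelled. At stake is how far the primary incidence figure, from a study done as a commitment to the regulator, can be trusted in the age group where outside care is most likely.

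**Working it through.** No stated sample size, power or alpha is at issue, so there is no plan figure to reproduce. The check sets the planned analyses side by side and then asks what their results could distinguish.

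**1. What changes between the two analyses**

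| | Main 60+ analysis | Dual-coverage subgroup |
|---|---|---|
| People | All eligible, 60 and over | VHA plus Medicare, found in claims, mainly 65 and over (9.2.3, 9.4) |
| Diagnoses: outcome, confirmation, clean window | CDW | CDW plus fee-for-service claims |
| Vaccination records | CDW | CDW plus the Medicare prescription file, which 9.4 says holds some ABRYSVO records |
| Weights | Main set | Refitted (9.7.3) |

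**2. Does any planned analysis hold the people fixed and change only the source?** None does.

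- Chart review (9.7.2.4) samples AF cases already identified in vaccinees and yields a positive predictive value. It cannot find missed cases.
- The priority group 1 subgroup also changes the people.
- The age bands deal with part of the age difference, not with coverage or source.
- The one sensitivity analysis named in 9.7.4 is negative control outcomes.

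**3. Incidence (illustration, assumed inputs).** Let c be the share of true new AF that CDW records, and f the share of CDW new-onset cases that are not new. Ignoring the small change in person-time,

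CDW rate / true rate = c / (1 - f).

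- Missed AF: assume 30-60% of first diagnoses in users of both systems are made outside VHA, none are missed in the other 47%, and AF incidence is equal in both. The missed share is 0.53 × 0.30 = 0.16 to 0.53 × 0.60 = 0.32, so c is 0.84 to 0.68.
- If half of the 60+ cohort has dual coverage and the rest are fully captured at the same AF rate, the shortfall in the main rate is 0.5 × 16% = 8% to 0.5 × 32% = 16%.
- Age mix: assume 15-25% of the 60+ cohort is aged 60-64 with half the AF rate. Even with perfect capture, the main rate lies 0.15 × 0.5 = 7.5% to 0.25 × 0.5 = 12.5% below a 65+ subgroup.
- The ranges 8-16% and 7.5-12.5% overlap. A main rate 10% below the linked subgroup fits either cause alone.
- Cancellation: with c = 0.84 and f = 0.16, the ratio is 0.84 / 0.84 = 1. Agreement would hide both errors.

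**4. Hazard ratio (illustration, assumed inputs).** Let d be the dual-coverage share, and s1 and s0 the CDW capture in dual-coverage vaccinees and controls, with full capture in everyone else:

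Main ratio = [d × HR(dual) × s1 + (1 - d) × HR(non-dual)] / [d × s0 + (1 - d)].

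Suppose the main ratio is 1.20, the linked-subgroup ratio is 1.50 and s0 = 0.70. Solve once for capture only (HR 1.50 in everyone, s1 unknown) and once for different people only (s1 = s0, HR in non-dual people unknown). The CDW-only ratio in the subgroup is 1.50 × s1 / s0. At d = 0.5 the two solutions are

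- s1 = [1.20 × 0.85 - 0.5 × 1.50] / (0.5 × 1.50) = 0.36, giving 1.50 × 0.36 / 0.70 = 0.77
- HR(non-dual) = [1.20 × 0.85 - 0.5 × 1.50 × 0.70] / 0.5 = 0.99.

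| d | Capture only: s1 | Its CDW-only subgroup ratio | Different people only: HR(non-dual) | Its CDW-only subgroup ratio |
|---|---|---|---|---|
| 0.5 | 0.36 | 0.77 | 0.99 | 1.50 |
| 0.7 | 0.47 | 1.02 | 0.71 | 1.50 |
| 0.9 | 0.54 | 1.15 | -0.69 (impossible) | not applicable |

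At d = 0.5 and 0.7 both explanations give the same two planned results, and a CDW-only run in the same subgroup separates them. At d = 0.9 different people alone cannot produce this gap. If s1 = s0 and the hazard ratio is the same in everyone, capture cancels and the main ratio is right.

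**The case against.** The protocol never says that a difference between the linked subgroup and the main result will be read as capture bias. A reader might infer that from section 9.9, where the linkage follows directly from the admission of incomplete data, but the stated purpose is only a fuller view of each person's care. Estimates in dual-coverage people are also a secondary objective in their own right. This stands: the plan commits no misreading. What remains is that the remedy offered for incomplete capture cannot measure it.

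A second objection is that a re-run under another data definition is a sensitivity analysis, which 9.7.4 leaves open for the SAP. The SAP may indeed add one. But the protocol itself fixes linkage as a change of people and data together, and that choice is open to comment.

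Third, mitigations exist. The limitation is disclosed, the priority group 1 and age subgroups help in part, baseline tables by subgroup would show how the people differ, and chart notes might reveal earlier AF. None of these gives a capture share.

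Fourth, a reader might infer that the hazard ratio is materially biased. The documents do not support that. The example in step 4 needs 36-47% capture in vaccinees against 70% in controls, no passage suggests such a gap, and the primary controls also have a recorded vaccination.

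**Conclusion.** The concern holds for incidence, the primary objective. The pair of results now planned cannot show how much missing outside care distorts the 60+ AF rate, in either direction. For the hazard ratio it matters mainly if capture differs between the compared cohorts.

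The size is unknown. The 16-32% and 7.5-12.5% ranges are illustrations: only the 53% is in the protocol, and it describes dually eligible Veterans two decades ago, not people with a VHA vaccination record. If nearly all of the 60+ cohort has dual coverage with fee-for-service claims, the difference in people shrinks and so does the problem. The protocol gives no such share.

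A reader might also infer that capture shares from the subgroup could simply correct the 60+ rate. They could not without assuming that capture in dual-coverage people carries over to people without Medicare, and that population difference is the one at issue here.

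**What to change.** In sections 9.2.3 and 9.7.3, specify that the dual-coverage subgroup is analysed with CDW data only and with CDW plus Medicare data:

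1. first with the individuals and index dates fixed;
2. then with exposure and clean-window eligibility re-derived from the linked data, since Medicare records can add vaccinations and earlier diagnoses.

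Report:

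- the share of linked-data AF cases that CDW captures;
- the share of CDW new-onset cases with AF or another supraventricular arrhythmia in Medicare claims during the clean window;
- incidence and hazard ratio both ways.

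Reword section 9.9 so that its description of linkage for adults from age 60 matches the subgroup-only wording of the Abstract, 9.2.3 and 9.4. Do not add a bias-corrected 60+ incidence unless it is labelled an exploratory sensitivity result that assumes subgroup capture carries over to the rest of the cohort.

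The cost is a few extra runs and tables on data already planned for linkage. The primary analysis does not change.

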9.5. Study Size

All individuals in the VHA database who meet the eligibility criteria as described in Section 9.2 will be included. The sample size achieved will depend on the number of individuals administered ABRYSVO identified within the VHA database during the study period, which will increase over time as the data will be analyzed at two different time points to add newly vaccinated individuals and matched controls.

9.5.1. Power

The study population will consist of VHA enrollees 18 years of age and older without a prior history of atrial fibrillation as assessed during a 2-year baseline period. Analysis will be conducted separately among individuals at least 60 years of age and among individuals 18-59 years of age.

Of the nine million VHA enrollees,²⁰ it is estimated that 56% are at least 60 years of age⁵⁹ and one million VHA enrollees have a prior history of atrial fibrillation.⁶⁰ Based on previous studies using VHA data, it is further estimated that 85% of the eligible population will have continuous enrollment during a 2-year baseline period.⁶¹ This results in approximately 3.8 million VHA enrollees at least 60 years of age estimated as eligible for inclusion in the study. Separately, approximately 11% of adults aged 18 to 49 and 29% of those aged 50 to 64 are immunocompromised or have a chronic condition that puts them at risk for severe RSV disease.⁶² As such, an estimated 330,000 to 868,000 VHA enrollees aged 18 to 59 may be eligible for inclusion in the study.

Table 2 illustrates the estimated sample size required for the weighted Cox regression using the internal comparator cohort design for individuals at least 60 years of age and for individuals 18-59 years of age, separately. For individuals at least 60 years of age, based on an expected background rate of 33.9 per 1,000 person-years for incident atrial fibrillation reported for male Medicare beneficiaries 65 years of age and older, assuming controls (vaccinated or unvaccinated) will be matched to ABRYSVO vaccinated individuals on a 4:1 ratio, a sample size of 37,444 and 116,493 individuals vaccinated with ABRYSVO is needed to detect a 2-fold and 1.5-fold increase in the IRR with a power of 80% and a one-sided alpha level of 0.05, respectively. For individuals 18-59 years of age, based on an expected

background rate of 4.4 per 1,000 person-years for incident atrial fibrillation reported for males 45-54 years of age⁶⁴ (which is assumed to comprise the majority of the 18-59 years age group as the VHA population is generally older) and assuming the same matching rate of controls to ABRYSVO vaccinated individuals (ie, 4:1 ratio), a sample size of 286,730 and 892,049 individuals vaccinated with ABRYSVO is needed to detect a 2-fold and 1.5-fold increase in the IRR, respectively, with a power of 80% and a one-sided alpha level of 0.05.63 Power of $\geq 80\%$ is typically desirable in drug safety research and the FDA views a risk ratio (RR) of >3 as meaningful, so these have also been used for the power calculations. The secondary objective's comparative analyses will only be conducted when a sufficient number of atrial fibrillation events have been observed for the analyses to be adequately powered.

Vaccine uptake will be monitored during the course of the study. If a sufficient number of atrial fibrillation events are not observed by the end of the planned study period, Pfizer will discuss contingency plans with the FDA to achieve the target sample size.

Table 2. Sample Size Calculations for the Weighted Cox Regression Using the Internal Comparator Cohort Design

Matching ratio (controls: ABRYSVO vaccinated)	IRR	Number of controls needed in each comparator cohort (N)	Number of ABRYSVO vaccinated individuals needed (N)
Individuals at leas	t 60 years of age		
4:1	1.2	2,413,066	603,267
	1.5	465,972	116,493
	2.0	149,777	37,444
	3.0	54,086	13,522
2:1	1.2	1,414,556	707,278
	1.5	266,270	133,135
	2.0	83,210	41,605
	3.0	29,124	14,562
Individuals 18-59	years of age		,
4:1	1.2	18,478,144	4,619,536
	1.5	3,568,194	892,049
	2.0	1,146,920	286,730
	3.0	414,166	103,542
2:1	1.2	10,832,015	5,416,008
	1.5	2,038,968	1,019,484
	2.0	637,178	318,589
	3.0	223,013	111,507

Table 2. Sample Size Calculations for the Weighted Cox Regression Using the Internal Comparator Cohort Design

Matching ratio		Number of controls	Number of ABRYSVO	
(controls:	IRR	needed in each	vaccinated individuals	
ABRYSVO		comparator cohort (N)	needed (N)	
vaccinated)		_		

Abbreviations: IRR, incidence rate ratio.

Notes:

The power calculations are based on assuming one-sided α =0.05, a power of 80%, and a risk interval of 4 days corresponding to the 0-3 day risk interval. A background rate of 33.9 incident atrial fibrillation events per 1,000 person years as observed among male Medicare beneficiaries 65 years of age and older was used for individuals at least 60 years of age, and a background rate of 4.4 incident atrial fibrillation events per 1,000 person years as observed among male 45-54 years of age was used for individuals 18-59 years of age.

Table 3 illustrates the estimated sample size required for the conditional Poisson regression using the SCRI design for individuals at least 60 years of age and for individuals 18-59 years of age, separately. For individuals at least 60 years of age, based on the expected background rate of 33.9 per 1,000 person-years for incident atrial fibrillation reported for male Medicare beneficiaries 65 years of age and older and a 4-day risk window (ie, days 0-3), a sample size of size of 38,453 and 129,204 individuals vaccinated with ABRYSVO is needed to detect a RR of 2 and 1.5, respectively, with 80% power and a one-sided alpha level of 0.05. ⁶⁶ For individuals 18-59 years of age, based on an expected background rate of 4.4 per 1,000 person-years for incident atrial fibrillation reported for male 45-54 years of age ⁶⁴ (which is assumed to comprise the majority of the 18-59 years age group) and a 4-day risk window (ie, days 0-3), a sample size of size of 294,458 and 989,381 individuals vaccinated with ABRYSVO is needed to detect a RR of 2 and 1.5, respectively, with 80% power and a one-sided alpha level of 0.05. ⁶⁶

Table 3. Sample size calculations for the conditional Poisson regression using the SCRI design

RR	Total number of events needed	Number of events expected in control interval	Number of ABRYSVO vaccinated individuals needed (N)	
Individuals at	Individuals at least 60 years of age			
Days 0-3 risk	interval			
1.2	787	467	718,310	
1.5	156	84	129,204	
2.0	53	25	38,453	
3.0	22	9	13,843	
Days 0-1 risk interval			,	
1.2	1,025	764	1,175,137	
1.5	197	138	212,263	

Table 3. Sample size calculations for the conditional Poisson regression using the SCRI design

RR	Total number of events needed	Number of events expected in control interval	Number of ABRYSVO vaccinated individuals needed (N)	
2.0	64	41	63,064	
3.0	24	13	19,996	
Days 0-30 risk	interval		,	
1.2	747	340	118,089	
1.5	153	62	21,534	
2.0	54	18	6,252	
3.0	23	6	2,084	
Individuals 18	3-59 years of age	1		
Days 0-3 risk i	interval			
1.2	787	467	5,500,485	
1.5	156	84	989,381	
2.0	53	25	294,458	
3.0	22	9	106,005	
Days 0-1 risk i	interval	1		
1.2	1,025	764	8,998,651	
1.5	197	138	1,625,411	
2.0	64	41	482,912	
3.0	24	13	153,118	
Days 0-30 risk	Days 0-30 risk interval			
1.2	747	340	904,273	
1.5	153	62	164,897	
2.0	54	18	47,873	
3.0	23	6	15,958	

Abbreviations: RR, risk ratio.

Notes:

Sample size calculations for the SCRI design were performed according to the method by Musonda et al.⁶⁷ The calculations are based on assuming one-sided α =0.05, a power of 80%, and the following scenarios: (1) a risk interval of 3 days and a control interval of 7 days (primary), (2) a risk interval of 2 days and a control interval of 7 days (secondary), (3) a risk interval of 31 days and a control interval of 31 days (secondary).

